6.2.2 Descriptive analyses

CRP and ferritin

Panels of individual spaghetti plots over time for CRP and ferritin will be provided using a logscale. The profiles of all participants in the respective treatment group will be included in these graphs as grey lines in the background and the respective individual participants profile will be plotted with darker color in the foreground. The respective applicable normal ranges will be added and it will be indicated by a symbol if a patient died.

Survival without the need for invasive mechanical ventilation

The numbers and percentages of responders will be calculated up to Day 15 and up to Day 29 respectively. It will be presented by treatment group together with the difference in response rates.

Improvement in clinical status

The numbers and percentages of responders will be calculated up to Day 15 and up to Day 29 respectively. It will be presented by treatment group together with the difference in response rates and a two-sided 90% CI based on Fishers exact test.

In addition a shift table of changes in response status will be provided with weekly time intervals (e.g. baseline, week 1, week 2, week 3 and week 4). For this the following response categories will be included:

- improvement of at least 1 step from baseline,
- no change from baseline
- worsening from baseline.

Also a stacked barchart illustrating the percentage of participants in each response categories as outlined above will be provided. Treatment groups will be presented next to each other. This will be provided for weeks 1, 2, 3 and 4.

For the subgroup analysis a shift table and stacked barchart for subgroup of participants with high baseline CRP by high and low corticosteroid dose during week 1 will be provided.

Clinical status over time

The 9-point ordinal scale will be summarized (mean, median, standard deviation, minimum, maximum, frequencies and percentages in each category) will be summarized by visit (including a time point for data from early discharge) and treatment group.

A stacked barchart illustrating the percentage of participants for each category of the 9-point ordinal scale with one bar will be provided. Treatment groups will be presented next to each other within one category. This will be provided for Day 8, Day 15, Day 21 and Day 29 (labeled as weeks 1, 2, 3 and 4).

The 9-point ordinal scale will also be plotted using a heat map with one row representing one patient and the score from baseline up to Day 29 visit will be shown by time using one unique color for each level of scale. The heat map will be plotted for each treatment group, within which patients will be sorted by the 9-point ordinal scale from high to low and by visit. The time when discharged from hospital will also be flagged on the plot. Values imputed by LOCF will be indicated by a different pattern (e.g. stripes) but the same color.

In addition a shift table and stacked barchart of changes between the categories of the 9-point scale will be provided with weekly time intervals (e.g. baseline, week 1, week 2, week 3 and week 4).

For the subgroup analysis a shift table and stacked barchart for subgroup of participants with high baseline CRP by high and low corticosteroid dose during week 1 will be provided.

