6.2 Secondary objectives

6.2.1 Variables

The following variables and corresponding objectives are classified as secondary pharmacodynamic endpoints and will be evaluated for their effect of MAS825 compared with placebo,

- On inflammatory status: Serum C-reactive protein (CRP) levels and ferritin
- On clinical status: Endpoints based on the 9-point ordinal scale:
- Survival without the need for invasive mechanical ventilation at Days 15 and 29 defined by a 9-point ordinal scale score of < 6 points at all time points
- At least one level improvement in clinical status at Days 15 and 29: defined as difference of ≥ 1 in the 9-point ordinal scale score of the screening value – Day 15 or Day 29 respectively.
- Clinical status over time

Missing data

For the clinical status 9-point ordinal scale missing values will be handled as follows:

- For participants who died prior to Day 29: The score for death will be imputed for all visits following the death up to and including Day 29.

For all other participants: LOCF will be applied up to and including Day 127. Following discharge or early discharge LOCF will be applied to all intermediate visits.

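### SAP 6.2.2 ties the 90% CI for a difference in improvement rates to Fisher's exact test, which bounds an odds ratio, and counts responders up to Days 15 and 29 where the endpoint is defined at those days

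*SAP*

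**What the plan says.** SAP 6.2.1 defines the improvement endpoint: "At least one level improvement in clinical status at Days 15 and 29: defined as difference of" at least 1 when the Day 15 or Day 29 score is subtracted from the screening score. SAP Table 1-1 and Protocol Table 2-1 also place the endpoint at Days 15 and 29. For deaths, 6.2.1 states that "The score for death will be imputed for all visits following the death up to and including Day 29"; the rule is addressed to participants who died before Day 29.

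SAP 6.2.2, under improvement in clinical status, gives the analysis: "The numbers and percentages of responders will be calculated up to Day 15 and up to Day 29 respectively". The result is shown by treatment group "together with the difference in response rates and a two-sided 90% CI based on Fishers exact test".

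The same counting sentence stands in the paragraph directly above, for survival without invasive ventilation. That endpoint is defined in 6.2.1 by a "9-point ordinal scale score of < 6 points at all time points".

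Nothing else in the visible text supplies an interval method. Protocol 12.5.1 leaves the analysis of hospital outcomes to the SAP, and SAP 6.2.3 gives a model only for CRP and ferritin.

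**The concern.** There are two separate faults in one paragraph.

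**Interval.** The estimate is a difference in two proportions. Fisher's test conditions on both margins of the 2 x 2 table, and the conditional distribution depends on the two rates only through the odds ratio. Inverting it therefore yields limits for the odds ratio and none for the difference. The programmer has to settle on some other interval, and the SAP does not say which.

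**Time basis.** 6.2.1 looks at the score on the target day. 6.2.2 counts up to that day, which suits the ventilation-free endpoint above because that one concerns all time points. For improvement, the phrase can be read as improvement at any visit by the target day. On that reading, a participant who improves on Day 6 and dies on Day 14 is a responder for Day 15, although under 6.2.1 the score is 8 and the participant is a non-responder.

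At stake are the limits and, possibly, the counts of one secondary comparison.

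**Working it through.** **Inputs.** 1:1 allocation (Protocol 6.1.3) and 60 per arm (Protocol 12.9.1). The documents give no response rate for improvement, so every responder count below is an assumption.

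**The plan's own figure.** The only power figure resting on this arm size for a clinical endpoint is the primary one: difference 3.6, SD 9.2, one-sided 10%. 3.6 / (9.2 x sqrt(2/60)) = 2.143; 2.143 - 1.282 = 0.862; power = 0.806, against 80% stated. It reproduces. No figure is stated for improvement, and the point does not depend on this one.

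**An odds-ratio limit does not fix a difference.** Take an upper limit of 4.15.
- Placebo rate 60%: odds 1.5 x 4.15 = 6.225; rate 6.225/7.225 = 86.2%; difference +26 points.
- Placebo rate 80%: odds 4 x 4.15 = 16.6; rate 16.6/17.6 = 94.3%; difference +14 points.

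**Intervals for the same 10-point difference** (6 of 60 participants; two-sided 90%). Fisher is the central interval from the noncentral hypergeometric distribution. The exact unconditional intervals invert two one-sided 5% tests, with the nuisance rate maximised.

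| MAS825 v placebo responders | Fisher: odds ratio | Miettinen-Nurminen: points | Exact, score-ordered: points | Exact, raw-difference-ordered: points |
|---|---|---|---|---|
| 36 v 30 | 0.77 to 2.93 | -5.0 to 24.5 | -5.3 to 25.0 | -5.8 to 25.4 |
| 42 v 36 | 0.77 to 3.15 | -4.4 to 24.0 | -4.8 to 24.7 | -5.8 to 25.4 |
| 48 v 42 | 0.78 to 3.80 | -3.1 to 22.9 | -3.3 to 23.2 | -5.8 to 25.4 |
| 54 v 48 | 0.83 to 6.47 | -0.8 to 21.1 | -0.9 to 21.3 | -5.8 to 25.4 |

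The Fisher column is on another scale. Between the two exact intervals for the difference, the lower limits are 5.8 - 5.3 = 0.5 points apart at a 50% placebo rate and 5.8 - 0.9 = 4.9 points apart at 80%. The word exact alone therefore does not determine the result.

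The choice can also change how a result reads. At an assumed 45 v 36, the Fisher odds-ratio interval is 0.97 to 4.15 and includes 1. Miettinen-Nurminen gives +0.9 to +28.6 points and excludes 0.

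**At versus up to.** Three kinds of participant who improve by at least one level before the target day:
- Screening 5, then 3, then 4 on Day 15: 5 - 4 = 1, a responder on either reading.
- Screening 5, then 4, then 5 or worse on Day 15: 5 - 5 = 0 or less, a non-responder under 6.2.1 but a responder if any visit counts.
- Screening 5, then 4, then death by Day 15: with a Day 15 score of 8, 5 - 8 = -3, a non-responder under 6.2.1 but a responder if any visit counts.

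Only the second and third kinds separate the readings. Each adds 1/60 = 1.7 points to its arm's rate. Equal numbers in both arms leave the difference unchanged; a net imbalance of 1 to 4 participants (assumed) moves it by 1.7 to 4/60 = 6.7 points.

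**The case against.** The strongest defence is that both phrases are loose drafting. The interval phrase may have been meant as an exact interval for the difference, and the time phrase may merely describe the data window. 6.2.1 holds the only definition of an improvement responder, and a programmer who applies it obtains the intended counts. The section is headed as descriptive, no hypothesis is attached to this endpoint, and Fisher's test remains valid for a p-value because an odds ratio of 1 and a difference of 0 are the same null. The Miettinen-Nurminen and score-ordered exact lower limits differ by only 0.1 to 0.4 points in the four examples.

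Most of this stands, and it rules out several stronger inferences:
- A reader might infer that the interval cannot be programmed at all. It can, once an unconditional method is chosen; the fault is that the named method does not match the estimate and no other is named.
- A reader might infer that *up to* misclassifies anyone who later worsens. Partial worsening leaves a responder under 6.2.1.
- A reader might infer a stated clash with the weekly shift table. That table ("In addition a shift table of changes in response status will be provided with weekly time intervals") has a category for "improvement of at least 1 step from baseline", but the day labels ("This will be provided for Day 8, Day 15, Day 21 and Day 29 (labeled as weeks 1, 2, 3 and 4") belong to a bar chart under clinical status over time. Equating week 2 with Day 15 in the shift table is reasonable but is not stated.
- A reader might infer that writing *at* settles every death. The death rule covers visits following a death before Day 29. It does not expressly cover a death on Day 15 for the Day 15 visit, or a death on Day 29; those rely on the score of 8 being recorded directly.

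The defence does not supply the missing interval method, and it does not explain why the text that specifies the table uses a different time basis from the definition.

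**Conclusion.** Both parts hold in limited form. Literally read, the planned interval is for the odds ratio while the reported estimate is a difference. If an exact unconditional interval was intended, the omitted ordering alone leaves the lower limit open by 0.5 to 4.9 points in the four examples. The time basis is an ambiguity rather than a proven contradiction: on the any-visit reading, each participant who improves and then loses the whole gain or dies adds 1.7 points to an arm's rate, and only an imbalance between arms reaches the difference.

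These sizes rest on 60 per arm and on assumed counts. The effect is confined to one descriptive secondary endpoint. The primary ANCOVA, its alpha and the sample size are untouched, and nothing here supports an inference that the trial's main conclusion is at risk. It is still worth correcting, because the endpoint is listed in the protocol and the repair is cheap.

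**What to change.** In the improvement paragraph of SAP 6.2.2:

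1. Replace the reference to Fisher's exact test with one named two-sided 90% interval for the rate difference, such as Miettinen-Nurminen or the exact unconditional interval ordered by the score statistic. If Fisher is to be kept, report the odds ratio with its Fisher interval instead.
2. Change *up to* to *at* for Day 15 and Day 29, and add that a death on or before the target day scores 8 and is a non-response.

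Leave the ventilation-free survival paragraph as it is; *up to* fits that endpoint.

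The cost is a few words in one paragraph and a standard interval routine, settled before database lock. No new data are needed.

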6.2.3 Statistical model, assumptions and hypotheses

CRP and ferritin

CRP levels are assumed to follow a log-normal distribution. Thus the log-transformed CRP data will be analyzed by fitting an MMRM model. Treatment, visit and their interaction as well as the three stratification factors will be included as fixed factors and baseline CRP as a covariate. Interactions between visit and each of the terms in the model will also be included. To model the dependency of observations an unstructured variance-covariance matrix will be fitted.

The analysis will be performed on the PD analysis set. The back-transformed geometric means for both treatment groups as well as the geometric mean ratios (MAS825 vs placebo) will be reported together with 90% confidence intervals (CIs) for each visit. The 1-sided p-value for the overall treatment factor will be reported. Ferritin levels will also be analyzed in the same manner.

For the subgroup analysis the same model as for the original MMRM analysis including in addition a factor for high vs. low corticosteroid use during week 1 (see [Section 7.2.2](#) for details) and its 3-way interaction with treatment and visit. The geometric means (+/-SE) per corticosteroid category and treatment group as well as the ratio of geometric mean (90% CI) per corticosteroid group are reported for each visit.

6.2.4 Model checking procedures

CRP and ferritin

The appropriateness of the log-normality assumption of CRP and ferritin values will be assessed by graphical mean e.g. residual plots.

6.2.5 Graphical presentation of results

CRP and ferritin

Estimated mean CRP +/- SE will be plotted over time by treatment group. The estimated geometric mean ratio to baseline in CRP +/- SE will also be presented. Ferritin levels will also be presented in the same manner.

For the subgroup analyses the following graphs will be provided:

- A line plot of the geometric means (+/-SE) are provided by corticosteroid dose category and treatment group together with the estimated values of the primary analyses by treatment group over time.

Side-by-side a second line plot on the treatment ratios (90% CI) per by corticosteroid dose category together with the estimated treatment difference (90% CI) of the primary analyses over time is given.

Survival without the need for invasive mechanical ventilation

Kaplan-Meier graphs with separate lines by treatment group will be provided for a graphical presentation. Participants will be censored discontinuing from the study or not experiencing an event.

6.3 Exploratory objectives

Commercially Confidential Information

Commercially Confidential Information

Commercially Confidential Information

7 Statistical methods for safety and tolerability data

All safety presentations and analyses will be based on the Safety Analysis Set.

7.1 Variables

Adverse events, vital signs (blood pressure, pulse rate, respiratory rate, body temperature, peripheral oxygen saturation, oxygen flow rate and/or FiO2), ECG intervals, safety laboratory measurements, as well as subject demographics, baseline characteristics, and treatment information.

7.2 Descriptive analyses

Safety summaries (tables, figures) include only data from the on-treatment period with the exception of baseline data, which will also be summarized where appropriate (e.g. change from baseline summaries).

The on-treatment period lasts from the date of administration of study treatment to Day 127.

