3. **Follow-up** (Day 16-29): After completion of the treatment period, patients will be observed until Day 29 or discharged from hospital, whichever is sooner. Study assessments to be conducted every 2 days for domiciled patients.

If patients are discharged from hospital prior to Day 29, a study visit conducted by telephone will occur on Day 29 (all other visits between discharge and Day 29 can be omitted).

4. **Safety follow-up visit assessment** (Day 45): A follow-up visit will be conducted at Day 45 if the patient is hospitalized. If patients are discharged from hospital prior to Day 45, a study visit will be conducted by telephone on Day 45.
5. **End of Study/Safety follow-up visit assessment** (Day 127): A follow-up visit for safety will be conducted at Day 127 if the patient is hospitalized. If patients are discharged from hospital prior to Day 127, a study visit will be conducted by telephone on Day 127.

4 Rationale

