2. Dose Reduced/increased
3. Drug interrupted/withdrawn

6. Its outcome (i.e., recovery status or whether it was fatal)

Conditions that were already present at the time of informed consent should be recorded in medical history of the participant.

Adverse events (including lab abnormalities that constitute AEs) should be described using a diagnosis whenever possible, rather than individual underlying signs and symptoms.

Adverse event monitoring should be continued until the end of study.

Once an adverse event is detected, it must be followed until its resolution or until it is judged to be permanent (e.g., continuing at the end of the study), and assessment must be made at each visit (or more frequently, if necessary) of any changes in severity, the suspected relationship to the interventions required to treat it, and the outcome.

Information about adverse drug reactions for the investigational drug can be found in the IB.

Abnormal laboratory values or test results constitute AEs only if they fulfill at least one of the following criteria:

- 1) they induce clinical signs or symptoms
- 2) they are considered clinically significant
- 3) they require therapy

Clinically significant abnormal laboratory values or test results must be identified through a review of values outside of normal ranges/clinically notable ranges, significant changes from baseline or the previous visit, or values which are considered to be non-typical in participant with the underlying disease.

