10.1.3 SAE reporting

To ensure participant safety, every SAE, regardless of causality, occurring after the participant has provided informed consent and until the last study visit must be reported to Novartis safety immediately, without undue delay, under no circumstances later than 24 hours of learning of its occurrence. Detailed instructions regarding the submission process and requirements are to be found in the investigator folder provided to each site.

Screen Failures (e.g. a participant who is screened but is not treated or randomized): SAEs occurring after the participant has provided informed consent until the time the participant is deemed a Screen Failure must be reported to Novartis.

All follow-up information for the SAE including information on complications, progression of the initial SAE and recurrent episodes must be reported as follow-up to the original episode immediately, without undue delay, under no circumstances later than 24 hours of the investigator receiving the follow-up information. An SAE occurring at a different time interval or otherwise considered completely unrelated to a previously reported one must be reported separately as a new event.

If the SAE is not previously documented in the Investigator's Brochure or Package Insert (new occurrence) and is thought to be related to the study treatment, a CMO & PS Department associate may urgently require further information from the investigator for health authority reporting. Novartis may need to issue an Investigator Notification (IN) to inform all investigators involved in any study with the same study treatment that this SAE has been reported.

Suspected Unexpected Serious Adverse Reactions (SUSARs) will be collected and reported to the competent authorities and relevant ethics committees in accordance with EU Guidance 2011/C 172/01 or as per national regulatory requirements in participating countries.

Any SAEs experienced after the last study visit should only be reported to Novartis Safety if the investigator suspects a causal relationship to study treatment.

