12.5.2 Safety endpoints

For all safety analyses, the safety set will be used. All listings and tables will be presented by treatment group.

Safety summaries (tables, figures) include only data from the on-treatment period with the exception of baseline data which will also be summarized where appropriate (e.g. change from baseline summaries). In addition, a separate summary for death including on treatment and post treatment deaths will be provided. In particular, summary tables for adverse events (AEs) will summarize only on-treatment events, with a start date during the on-treatment period (treatment-emergent AEs).

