7.2.6 Adverse events

All information obtained on adverse events will be listed by treatment and subject.

Summary tables for adverse events (AEs) will summarize only on-treatment events, with a start date during the on-treatment period (treatment-emergent AEs).

The number and percentage of subjects with adverse events will be tabulated by body system and preferred term with a breakdown by treatment. Separate summaries will be provided for study medication related adverse events and other significant adverse events leading to discontinuation.

The number of deaths resulting from SAEs suspected to be related to study treatment and SAEs irrespective of study treatment relationship will be provided by SOC and PT until day 29 and after day 29.

The number of deaths resulting from SAEs suspected to be related to study treatment and SAEs irrespective of study treatment relationship will be provided by PT until day 29 and after day 29.

A subject with multiple adverse events within a body system is only counted once towards the total of this body system and treatment.

For the legal requirements of ClinicalTrials.gov and EudraCT, two tables are required:

on treatment emergent adverse events which are not serious adverse events and on treatment emergent serious adverse events and SAE suspected to be related to study treatment will be provided by system organ class and preferred term on the safety analysis set.

If for a same patient, several consecutive AEs (irrespective of study treatment causality, seriousness and severity) occurred with the same SOC and PT:

- a single occurrence will be counted if there is ≤ 1 day gap between the end date of the preceding AE and the start date of the consecutive AE
- more than one occurrence will be counted if there is > 1 day gap between the end date of the preceding AE and the start date of the consecutive AE.

For occurrence, the presence of at least one SAE / SAE suspected to be related to study treatment / non SAE has to be checked in a block e.g., among AE's in a ≤ 1 day gap block, if at least one SAE is occurring, then one occurrence is calculated for that SAE.

The SAEs and deaths by State will be graphically presented in a barchart. Refer to [Section 10.8](#) for details on the state.

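### SAP 7.2 closes the on-treatment period at Day 127, so on a calendar reading new AEs and SAEs on Days 128–134 are collected and listed but left out of the summary tables

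*SAP*

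**What the plan says.** **Analysis period.** SAP 7.2 restricts the safety output: "Safety summaries (tables, figures) include only data from the on-treatment period with the exception of baseline data". It then fixes the end of the period: "The on-treatment period lasts from the date of administration of study treatment to Day 127". It gives no visit window and no reference to the actual last visit. SAP 7.2.6 applies the restriction to adverse events by onset: "Summary tables for adverse events (AEs) will summarize only on-treatment events, with a start date during the on-treatment period".

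**Protocol analysis text.** Protocol 12.5.2 carries the same restriction ("Safety summaries (tables, figures) include only data from the on-treatment period") but gives no end day. Protocol 12.5.2.1 describes treatment-emergent events as those starting or worsening after dosing, also without an upper day. In the visible text the Day 127 limit therefore comes from the SAP alone.

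**Data collection.** Protocol Table 8-1 schedules the end-of-study visit at Day 127 with a window of plus or minus 7 days. Protocol 10.1.1 says "Adverse event monitoring should be continued until the end of study". Protocol 10.1.3 covers every SAE "occurring after the participant has provided informed consent and until the last study visit must be reported". For discharged participants the final contact is a call (Protocol 3): "If patients are discharged from hospital prior to Day 127, a study visit will be conducted by telephone on Day 127". Footnotes 3 and 4 to Table 8-1 include adverse events among the items obtained by phone.

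**The concern.** The collection period follows the participant's actual last contact, while the tabulation period stops on a fixed day that lies in the middle of the allowed window. A participant seen or called on, say, Day 132 is fully compliant, and the site must record any event up to that day. Taken literally, the SAP then keeps a new event from Days 128–132 out of the AE and SAE tables.

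Counts of participants with AEs and SAEs are a secondary safety endpoint (Protocol Table 2-1, SAP Table 1-1). SAP 7.2.6 also builds the ClinicalTrials.gov and EudraCT tables on treatment-emergent events, so the omission would carry over to public reporting. As written, a programmer must either leave out valid data or depart from the SAP.

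**Working it through.** The plan's figure here is a day cut-off, so there is no power or sample-size result to reproduce. The check is day arithmetic.

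**Inputs**
- End of on-treatment period: Day 127 (SAP 7.2)
- Final visit window: Day 127 ± 7 (Protocol Table 8-1)
- AE/SAE collection: to the actual last visit (Protocol 10.1.1 and 10.1.3)
- Rule for AE tables: start date within the period (SAP 7.2.6)
- Planned size: 60 per arm (Protocol 12.9.1)

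**Step 1: the window.** 127 − 7 = 120 and 127 + 7 = 134, so Days 120–134, which is 134 − 120 + 1 = 15 allowed days. Those after the cut-off are Days 128–134, which is 7 days.

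**Step 2: onset days collected but not tabulated.** For a final contact on day d, this is max(0, d − 127).

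| Final contact | AE/SAE collection runs to | Tables accept onset to | Collected, not tabulated |
|---|---|---|---|
| Day 120 | Day 120 | Day 127 | 0 days |
| Day 127 | Day 127 | Day 127 | 0 days |
| Day 130 | Day 130 | Day 127 | 3 days |
| Day 134 | Day 134 | Day 127 | 7 days |

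**Step 3: size.** The maximum is 7 days, or 7/134 = 5% of the follow-up of a participant last seen on Day 134. The documents do not give the distribution of visit days. Purely as an illustration, if final contacts were spread evenly over the 15 days, the mean loss over all participants would be (1 + 2 + … + 7)/15 = 28/15 = 1.9 days, about 1.5% of 127.

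**Step 4: what one event would do.** If one omitted SAE were that participant's only SAE, the arm's proportion with an SAE would move by 1/60 = 1.7 percentage points. The expected number of such events cannot be computed from the documents.

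**Step 5: where the period should end.** Ending it at the actual final contact would cover Days 128–134, but would shorten it for participants seen on Days 120–126. Protocol 10.1.3 still has SAEs reported after the last visit when a causal relationship is suspected. Such an SAE on Day 125, after a final call on Day 122, is inside the present period and would fall outside one that ends at the call. Taking the later of Day 127 and the final contact avoids this: no onset day up to Day 127 is lost, and none of the 7 later window days is excluded for participants seen on them.

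**The case against.** The strongest reply is that Day 127 is the name of a visit throughout both documents. Examples are the study design text, the disposition categories in SAP 7.2.1 and the carry-forward rule in SAP 6.2.1. Vital signs, ECGs and laboratory values are summarized by visit (SAP 7.2.3 to 7.2.5), so an in-window final visit would naturally stay under its Day 127 label. This largely stands for by-visit data. It does not settle the AE rule, because a start date has to be compared with a calendar limit.

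A second reply is that a visit window and an analysis period serve different purposes, and that a fixed upper limit is a legitimate way to equalize follow-up. That is fair as a principle. The SAP, however, does not present the limit as such a choice, and the limit cuts through data that the protocol requires.

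Third, parts of the SAP are redacted and may hold a windowing rule. This cannot be excluded, although SAP 7.2 points to none.

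A reader might also infer more than the text supports:
- *That late events vanish from the report.* They do not. The restriction covers tables and figures, while SAP 7.2.6 lists all AE information. Protocol 12.5.2 adds a death summary that includes post-treatment deaths, and the SAP's death tables after Day 29 state no upper day. An event that began by Day 127 but is first reported on a later call stays in the tables.
- *That 7/15 = 47% of end-of-study data are lost.* That is a share of allowed days, not of participants, and most final contacts are likely to be calls without measurements.
- *That end-of-study laboratory and vital-sign results are generally excluded.* Discharged participants have a phone contact only. For those still in hospital, footnote 4 to Table 8-1 asks for assessments on the scheduled visit day.
- *That a stated risk control is undermined.* Protocol 4.6.2 and 4.7 name frequent follow-up and a minimal study duration, not long follow-up.

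**Conclusion.** The mismatch is real and small. On a calendar reading of Day 127, new AEs and SAEs with onset on Days 128–134, in participants whose compliant final contact comes after Day 127, are collected and listed but not summarized in the AE/SAE tables. The loss is at most 7 days of onset time per affected participant. Listings are unaffected and deaths largely so. Laboratory and vital-sign summaries are affected at most for the few participants still hospitalized, and only if Day 127 is not the visit label.

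The conclusion rests on two assumptions: that Day 127 in SAP 7.2 is a study day, as a start-date rule needs, and that no redacted text extends the period. The primary analysis is not touched. This is a cheap improvement, not a threat to the safety conclusions.

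**What to change.** In SAP 7.2, define the on-treatment period as running from study drug administration to Day 127 or the participant's actual end-of-study visit or call, whichever is later. Add that final visits within the ±7-day window are summarized under Day 127. SAP 7.2.6 then needs no change, because it refers to the same period.

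The cost is one phrase and one clarifying sentence, with no change to procedures, data collection or efficacy analyses. The small downside is that the length of the tabulated period varies by up to 7 days between participants.
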